3.1.5 Post-Treatment Follow-up Period

Subjects will attend a Follow-up Visit ~14 weeks after each subject's final treatment period visit; however, the Follow-up Visit may be waived in place of a telephone contact, at the discretion of the investigator.

3.2 Dose and Dosing Regimen

3.2.1 Treatment Period 1

The first 32 subjects with C1-INH HAE who are eligible to participate in Treatment Period 1 will be randomly assigned to receive 1 of the following treatment regimens in a blinded manner:

- A single loading dose of [REDACTED] mg CSL312 IV followed ~1 week later by [REDACTED] mg CSL312 q4wk SC.
- A single loading dose of [REDACTED] mg CSL312 IV followed ~1 week later by [REDACTED] mg CSL312 q4wk SC.
- A single loading dose of [REDACTED] mg CSL312 IV followed ~1 week later by [REDACTED] mg CSL312 q4wk SC.
- A single loading dose of placebo IV followed ~1 week later by placebo q4wk SC.

After the first 32 subjects with C1-INH HAE are randomly assigned to treatment (as above), up to an additional 8 subjects will be assigned in an open-label manner to receive

[REDACTED] mg CSL312 q2wk SC. [REDACTED]

Up to 10 eligible subjects with FXII/PLG HAE will be assigned in an open-label manner to receive a loading dose of [REDACTED] mg CSL312 IV followed ~1 week later by [REDACTED] mg CSL312 q4wk SC.

All IV loading doses of investigational product (ie, CSL312 or placebo) will be administered by the investigator or delegate at the study site. All SC doses of investigational product will be self-administered under supervision of the investigator or delegate at the study site.

Subjects should remain on site for at least 30 minutes after the investigational product is administered.

Dose modification is NOT permitted in Treatment Period 1, and additional details are presented in [Section 5.5](#).

Additional information related to dosing and administration of investigational product is presented in [Section 6.2](#).

3.2.2 Treatment Period 2

C1-INH HAE subjects who continue to participate in Treatment Period 2 will be receiving CSL312 [REDACTED] mg or [REDACTED] mg q4wk SC at the beginning of Treatment Period 2. Effective with Amendment 2, all C1-INH HAE subjects receiving the [REDACTED] mg dose will have their dose reduced to [REDACTED] mg q4wk SC at their next scheduled study visit. FXII/PLG HAE subjects will be maintained on the [REDACTED] mg q4wk SC dose. The first dose of CSL312 in Treatment Period 2 will be administered at the Week 13 (Day 91) Visit and at the Week 13 (Day 85) Visit for subjects who administer investigational product q4wk and q2wk in Treatment Period 1, respectively. Administration of CSL312 at the Week 13 (Day 85 / 91) Visit, the Week 17 (Day 119) Visit, and the Week 21 (Day 147) Visit will be self-administered under supervision of the investigator or delegate at the study site. After administration of the CSL312 at the Week 21 (Day 147) Visit, all subsequent doses of CSL312 will be self-administered SC every 28 days (\pm 2 days) by the subject at home or at the study site.

Subjects should remain at the study site for at least 30 minutes after any CSL312 administration that occurs at the study site.

Dose modification details for Treatment Period^o2 are presented in [Section 5.5](#).

Additional information related to dosing and administration of investigational product is presented in [Section 6.2](#).

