- ^e At visits where physical examinations, vital signs, urine collection, and blood draws are scheduled to occur on the same day as administration of CSL312, administration of CSL312 will occur after these assessments have been completed.
- ^f The test for beta-human chorionic gonadotropin will be performed for women of childbearing potential (only). A serum or urine pregnancy test may be used. A serum pregnancy test will be performed by the site if urine result is inconclusive.
- ^g Subjects may use the on-demand medication of their choice to treat HAE attacks experienced during the study if that medication has previously been shown to be effective (see [Section 7.2](#)).
- ^h The first administration of investigational product in Treatment Period 2 will occur at the Week 13 (Day 85 / 91) Visit. Investigational product will be self-administered by the subject under the supervision of the investigator or delegate at the Week 13 (Day 85 / 91) Visit, the Week 17 (Day 119) Visit, and the Week 21 (Day 147) Visit. After administration of the investigational product at the Week 21 (Day 147) Visit, all subsequent doses of investigational product will be self-administered SC every 28 days (\pm 2 days) by the subject at home or at the study site.
- ⁱ The Treatment Period 2 Follow-up Visit may be waived in place of a telephone contact. If the Treatment Period 2 Follow-up is conducted as a visit, then a blood draw for assessment of PK / [redacted] should occur.
- ^j Investigational product will be dispensed and accountability will be conducted only if Treatment Period 2 is extended beyond the subject's Week 57 (Day 399) Visit (see [Section 8.5.4.14](#)).

Table of Contents

List of Personnel and Organizations Responsible for Conduct of the Study.....	2
Revision History	3
Protocol Synopsis	4
Schedule of Assessments: Screening and Run-in Period [All Subjects]	15
Schedule of Assessments: Treatment Period 1 [C1-INH HAE and FXII/PLG HAE Subjects Receiving Investigational Product Every 4 Weeks]	17
Schedule of Assessments: Treatment Period 1 [C1-INH HAE Subjects Receiving Investigational Product Every 2 Weeks].....	19
Schedule of Assessments: Treatment Period 2 [All Subjects].....	21
Table of Contents	23
List of Tables.....	28
List of Figures	28
List of Appendices	28
List of Abbreviations	29
List of Conventions.....	31
1 Introduction	32
1.1 Background	32
1.1.1 Factor XII	32
1.1.2 Factor XII and the Kallikrein-kinin Pathway	32
1.1.3 Hereditary Angioedema.....	32

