Vz	Volume of distribution during the elimination phase
CCI	CCI

List of Conventions

- The abbreviation “C1-INH HAE” is used in this clinical study protocol to include hereditary angioedema type 1 (quantitative decrease in C1-esterase inhibitor plasma concentrations) and hereditary angioedema type 2 (dysfunctional C1-esterase inhibitor present in normal or high plasma concentrations).
- The abbreviation “FXII/PLG HAE” is used in this clinical study protocol to include hereditary angioedema with normal C1-esterase inhibitor and factor XII or plasminogen gene mutation.
- In some sections of the protocol, dosing regimens are identified without reference to the initial intravenously administered loading dose that some subjects are required to receive. This approach has been taken to streamline presentation of protocol text and is not intended to indicate that the loading dose is optional. Full details for dosing and administration are presented in [Section 3.2](#), with supportive information presented in [Section 5.5](#) and [Section 6.2](#).
- For subjects who administer investigational product subcutaneously every 4 weeks in Treatment Period 1, the first dose of CSL312 in Treatment Period 2 will be administered at the Week 13 (Day 91) Visit. For subjects who administer investigational product subcutaneously every 2 weeks in Treatment Period 1, the first dose of CSL312 in Treatment Period 2 will be administered at the Week 13 (Day 85) Visit. Within the body of the protocol, these visits are presented together as “the Week 13 (Day 85 / 91) Visit”.

1 Introduction

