6.1.2 Randomization Procedures

Randomization will be conducted using an IRT. The investigator will be supplied with a user guide for the IRT. The randomization list will be generated according to the approved randomization specifications. The IRT service provider will keep the randomization code on file.

Treatment Period 1

In Treatment Period 1, subjects will be randomized using block randomization with fixed block size by means of centralized IRT to 1 of 4 blinded treatment arms:

- The first 32 subjects with C1-INH HAE who are assigned to treatment in Treatment Period 1 will be randomized in a 1:1:1:1 ratio to receive placebo, [REDACTED] mg CSL312, [REDACTED] mg CSL312, or [REDACTED] mg CSL312 q4wk SC.

Up to 8 additional subjects with C1-INH HAE who are assigned to treatment in Treatment Period 1 after the first 32 subjects (above) will receive [REDACTED] mg CSL312 q2wk SC.

Subjects with FXII/PLG HAE who are assigned to treatment in Treatment Period 1 will receive [REDACTED] mg CSL312 q4wk SC.

Treatment Period 1 will be conducted in a blinded manner for C1-INH HAE subjects who receive placebo, [REDACTED] mg CSL312, [REDACTED] mg CSL312, or [REDACTED] mg CSL312 q4wk. Emergency unblinding will be performed in the IRT ([Section 6.1.3.2](#)).

Treatment Period 1 will be conducted in an open-label manner for C1-INH HAE subjects who receive [REDACTED] mg CSL312 q2wk and for FXII/PLG HAE subjects who receive [REDACTED] mg CSL312 q4wk.

Treatment Period 2

In Treatment Period 2, subjects will be re-randomized using block randomization with fixed block size by means of a centralized IRT to receive either [REDACTED] mg or [REDACTED] mg CSL312 q4wk.

- For subjects with C1-INH HAE, randomization will be stratified by Treatment Period 1 treatment assignments: subjects on placebo q4wk; subjects on [REDACTED] mg CSL312 q4wk; subjects on [REDACTED] mg CSL312 q2wk.
 - Subjects on placebo q4wk in Treatment Period 1 will be randomized in a 1:1 ratio to receive either [REDACTED] mg CSL312 q4wk or [REDACTED] mg CSL312 q4wk in Treatment Period 2.
 - Subjects on [REDACTED] mg CSL312 q4wk in Treatment Period 1, will be randomized in a 1:1 ratio to receive either [REDACTED] mg CSL312 q4wk or [REDACTED] mg CSL312 q4wk in Treatment Period 2.
 - Subjects on [REDACTED] mg CSL312 q2wk in Treatment Period 1 will be randomized in a 1:1 ratio to receive either [REDACTED] mg CSL312 q4wk or [REDACTED] mg CSL312 q4wk in Treatment Period 2.

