8.5.4.2 Week 17 (Day 119) Visit

The following procedures will be conducted at the Week 17 (Day 119) Visit:

- Physical examination.
- Vital signs, including weight.
- Collection of urine for urinalysis.
- Collection of urine or blood for pregnancy test (for women of childbearing potential). A serum pregnancy test will be performed by the site if urine result is inconclusive.
- Collection of blood to assess:
 - Hematology.
 - Biochemistry.
 - Coagulation.
 - PK / [REDACTED]
- Review eDiary data, including investigator assessment of HAE symptoms and documentation of HAE attacks.
- Confirm access to on-demand HAE medication.
- Supervise subject self-administration CSL312 (SC).
- Dispense CSL312.
- Accountability of CSL312.

- Concomitant medications and therapies.
- Adverse events.

Note: The physical examinations, vital signs, weight measurement, and collection of blood and urine for laboratory assessments must occur before administration of the investigational product.

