## 12.2 Summary of CSL312 Plasma Concentrations

The handling and imputation of BLQ values for PK parameter derivation is described in PK-GDL-01. The imputation rules below will be used for summary statistics of CSL312 plasma concentrations. The summaries will be given by sampling time point (planned time points) and treatment group.

- The sampling time of pre-dose samples relative to start of the dose infusion will be treated as zero;
- Concentration values below BLQ in pre-dose samples and in samples taken before the time of the first quantifiable concentration will be treated as zero;
- Post-dose one or more consecutive BLQ concentrations flanked by quantifiable concentrations will be set to missing;

- Post-dose BLQ concentrations after the last quantifiable point will be set to missing for mean presentations of plasma concentrations.
- The mean/median value at a time-point where one or more samples have BLQ values will be reported (in tabular or graphical fashion) even if the mean/median value is below the lower limit of quantification (BLQ) of the assay;
- Zero mean or median values will be included in summary tables.

It should be noted that a high proportion of BLQ values may affect the SD; if more than 50% of the values are imputed (i.e., BLQ), then the SD will not be displayed.

Summary statistics for concentration-time data will include the percentage of BLQ values relative to the total number of observations

$$\%BLQ = 100 * (\text{number of subjects who have BLQ values} / \text{total number of subjects within each treatment group at each time point})$$

and the coefficient of variation (CV) % in addition to the statistic parameters outlined in Section 7.

Two mean plots for CSL312 plasma concentrations (one on linear and one on log-linear scale) versus nominal (planned) time will be provided. All CSL312 treatment groups will be overlaid in each mean plot. Error bars on mean values within the plot will represent +/- SD values. The plasma concentration for subjects who are down-titrated from [redacted] mg to [redacted] mg will stop for the [redacted] mg group when down-titration occurs. The plasma concentrations after down-titration will be included in the [redacted] mg group starting at the time point of down-titration.

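### Former q2wk subjects are put on a q4wk regimen in Treatment Period 2, but their first two doses there are scheduled a nominal 34 days apart, and Week 17 summaries by planned time pool them with 28-day samples

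*Protocol*

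**What the plan says.** **Regimen.** Protocol 6.1.2 states that subjects on the (redacted) "mg CSL312 q2wk in Treatment Period 1 will be randomized in a 1:1 ratio to receive either [REDACTED] mg CSL312 q4wk" or a second dose level on the same four-weekly schedule. Protocol 3.1.4 and SAP 4.4 agree.

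**Start of TP2.** The protocol's List of Conventions sets two start days. For subjects from the four-weekly arms, "the first dose of CSL312 in Treatment Period 2 will be administered at the Week 13 (Day 91) Visit". For subjects from the q2wk arm, "the first dose of CSL312 in Treatment Period 2 will be administered at the Week 13 (Day 85) Visit". The synopsis and section 3.2.2 repeat this.

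**Later doses.** The synopsis and footnote h of the TP2 schedule give one list of supervised dosing visits for everyone: "at the Week 13 (Day 85 / 91) Visit, the Week 17 (Day 119) Visit, and the Week 21 (Day 147) Visit". Section 8.5.4.2 has a single entry, "The following procedures will be conducted at the Week 17 (Day 119) Visit", with no other day for the former q2wk arm. In section 3.2.2, the doses on these shared days "will be self-administered under supervision of the investigator or delegate at the study site. After administration of the CSL312 at the Week 21 (Day 147)", an interval of 28 days applies, with a tolerance of 2 days either way; it is stated only for doses after Week 21.

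**Sampling and analysis.** Under section 8.5.4.2, Week 17 blood is drawn before that visit's dose. SAP 7 keeps the q2wk arm apart in Treatment Period 1 (TP1) only and reports C1-INH subjects in TP2 by TP2 dose. On concentrations, SAP 12.2 says "The summaries will be given by sampling time point (planned time points) and treatment group". SAP 11.10 summarises laboratory tests by scheduled visit. SAP 7 and 8.2.6 apply no visit windows.

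**The concern.** The two start days are six days apart, but the following visits are common to all subjects. The first TP2 interval therefore cannot have the same nominal length for both groups. The week labels hide this: Days 85 and 91 both fall in Week 13 and Day 119 falls in Week 17, so the schedule looks four weeks apart for everyone.

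Two things are at stake. First, a site treating a former q2wk subject has a stated four-weekly regimen and a visit calendar that disagree on nominal days, at the moment when the subject moves from two-weekly to four-weekly dosing. No reason for a longer first interval is given. Second, the Week 17 pre-dose sample is taken a nominal 34 days after the last dose in these subjects and 28 days after it in the rest, and the SAP reports both under one planned time point within each TP2 dose group.

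**Working it through.** **Inputs.** First TP2 dose on Day 91 or Day 85 (Protocol List of Conventions, 3.2.2). Next doses on Days 119 and 147 (3.2.2, 8.5.4). q4wk means every 4 weeks, or 4 × 7 = 28 days. Up to 8 q2wk subjects (3.5). Half-life about 19 days (1.2.3.1), used only to size the effect.

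**Step 1: reproduce the stated interval.** From the four-weekly arms: 119 − 91 = 28 and 147 − 119 = 28. The q4wk label reproduces.

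**Step 2: the former q2wk arm.** 119 − 85 = 34, then 147 − 119 = 28. The label does not reproduce for the first interval, which is 34 / 28 = 1.21 times the stated one.

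**Step 3: was another visit adjusted for this arm?** Yes. TP1 follow-up is on Day 180 for the q2wk arm and Day 186 for the others: 180 − 85 = 95 and 186 − 91 = 95. The six-day offset was carried into that visit but not into Days 119 and 147.

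**Step 4: could tolerances absorb it?** The stated tolerance applies only after Week 21; if borrowed, its upper limit is 28 + 2 = 30, which is 4 days short of 34. The TP2 schedule table is not legible in the text available, so its visit windows are unknown; this is not counted as an omission from the plan. As an assumption, take ± 3 days at both visits, as used for the run-in contacts and the TP1 follow-up. The interval then runs from 116 − 88 = 28 to 122 − 82 = 40 days. It reaches 28 only if the first dose is as late, and the second as early, as allowed.

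**Step 5: effect on one subject's pre-dose level.** Assuming mono-exponential decline, the ratio of the 34-day to the 28-day value is 2^(−6/h), where h is the half-life in days.

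| Half-life h (days) | Ratio | Reduction |
|---|---|---|
| 15 (assumed) | 0.76 | 24% |
| 19 (stated) | 0.80 | 20% |
| 23 (assumed) | 0.83 | 17% |

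Under a simple repeated-bolus version of this model, the ratio at the Week 21 pre-dose sample is about 0.91 to 0.95, so the difference fades.

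**Step 6: share of each pooled group.** Suppose every planned subject continues, before any Amendment 2 dose reduction. Each TP2 dose group then holds 8 subjects continuing their dose, 8 / 2 = 4 from placebo, 8 / 2 = 4 from the re-randomised four-weekly arm and 8 / 2 = 4 from the q2wk arm. The q2wk share is 4 of 20.

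**The case against.** The strongest reply is that this is a small feature of an open-label extension and that the SAP already contains most of its consequences. Several stronger readings that a reader might infer do fail.

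- *Attacks late in the 34-day interval distort efficacy.* They do not. SAP 8.2.8 lists, but does not analyse, attacks starting between Day 85/91 and Day 147, and TP2 efficacy begins at Day 147.
- *There is no way for these subjects to have a 28-day interval.* The documents do not support this. The windows are unknown, and ± 3 days at both visits would just reach 28. The contradiction holds on nominal days.
- *Week 17 summaries fail to describe the q4wk regimen because of these six days.* Week 17 is mixed anyway. Former placebo subjects enter the same dose groups with no intravenous loading in TP2 (Protocol Table 5), so Week 17 follows their first active dose. Under the same simple model their trough would be 1 − 2^(−28/19) = 64% of the steady-state trough, a larger shortfall than 20%.
- *The pooled Week 17 mean is 20% too low.* The 20% compares the same subject at two times. Former q2wk subjects also carry over drug from two-weekly dosing at a redacted dose, so whether their Day 119 level lies above or below that of the others cannot be determined.

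It is also fair that q4wk is used loosely elsewhere: in TP1 the first two subcutaneous doses fall on Days 6 and 35, which is 29 days. PK parameters, individual plots and concentration listings use actual times (SAP 7, 12, 12.2), and the secondary PK endpoints concern TP1 only (Protocol Table 2).

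These points limit the consequence. They do not reconcile the passages: a one-day departure is not a six-day one, and nothing in the text presents 34 days as intended.

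**Conclusion.** The point holds as an exact contradiction on nominal visit days. Up to 8 open-label subjects are assigned a four-weekly regimen while the calendar puts their first two TP2 doses 34 days apart, against 28 days for all other subjects.

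The analytic consequence is confined to Week 17 summaries by planned time: the concentration table and mean plots of SAP 12.2 and the laboratory summaries of SAP 11.10. These pool 34-day and 28-day pre-dose samples within each TP2 dose group. The within-subject effect on concentration is a reduction of about 20% (17% to 24% for half-lives of 23 down to 15 days). It rests on mono-exponential decline, doses given on the nominal days and all else equal. The net bias in the pooled summary cannot be derived from the documents.

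The primary comparison, the TP2 efficacy summaries, the secondary PK endpoints and the PK parameter derivations are unaffected. Former q2wk subjects change regimen, so they are also outside the combined TP1 and TP2 analysis. This is a matter of schedule consistency and PK reporting, not a threat to the trial's conclusions.

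**What to change.** 1. **Protocol.** Reconcile three items for subjects coming from the q2wk arm: the Day 85 start, the shared Day 119 and Day 147 visits, and the stated q4wk interval. The places are the synopsis, section 3.2.2, section 8.5.4 and footnote h of the TP2 schedule. The sponsor decides which governs. If the longer first interval is intended, say so and give the reason.
2. **SAP 12.2.** Present the Week 17 pre-dose concentrations of former q2wk subjects separately, or tabulate Week 17 by actual days since the last dose. A footnote to the Week 17 laboratory summaries can note the different interval.

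The cost is one protocol clarification and one extra line in a summary. No new visits, samples or subjects are needed. Splitting the group leaves at most about 8 / 2 = 4 subjects per dose on that line, so it should be read descriptively.

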3.3 Scientific Rationale

3.3.1 Study Design Rationale

The present phase 2 study will evaluate the efficacy, safety, tolerability, and PK profile of multiple subcutaneous administrations of CSL312 across a range of doses in subjects with C1-INH HAE or FXII/PLG HAE. The study consists of a Screening Period to assess subject eligibility, a Run-in Period to assess underlying disease activity, and 2 treatment periods to assess initial and long-term (respectively) safety, tolerability, and efficacy. The data from this study will be used to select dose(s) for a potential phase 3 study.

3.3.2 Dose Rationale

Dose selection was based on the safety, PK and [REDACTED] data obtained in the phase 1 single ascending dose study (Study 1001) after administration of single IV and SC doses ranging from 0.1 to 10 mg / kg (7.75 to 1015 mg) in healthy volunteers. The key [REDACTED] endpoint used

for dose selection was CCI [REDACTED]. It is hypothesized that inhibiting CCI [REDACTED] consistently to a particular % target inhibition is expected to provide protection from HAE attacks. The exact % target CCI [REDACTED] to prevent HAE attacks is unknown and will be evaluated in this study in HAE patients.

A PK / CCI [REDACTED] model was developed to quantify the relationship between CSL312 plasma concentrations and CCI [REDACTED] from the IV and SC cohorts in Study 1001. The modeled relationship showed an increase in inhibition of CCI [REDACTED] with increasing concentrations of CSL312. The IC50 was estimated to be 14.9 µg / mL.

Based on the relationship between CSL312 plasma concentration and CCI [REDACTED] the % target inhibition levels that were chosen included ≥ 30 , ≥ 50 , and $\geq 90\%$ (corresponding to doses that would result in inhibition below the IC50, at the inflection point and at the maximum effect of the curve), which would provide information along the entire spectrum of the curve allowing for a robust assessment of doses in this study. Simulations using the final PK / CCI [REDACTED] model determined that fixed doses of CCI [REDACTED] mg, CCI [REDACTED] mg, and CCI [REDACTED] mg administered every 4 weeks would result in at least 75% of the patients reaching a % target inhibition of CCI [REDACTED] of ≥ 30 , ≥ 50 , and $\geq 90\%$, respectively.

The dosing interval of every 4 weeks was selected based on the calculated half-life of CSL312 of ~19 days in the phase 1 single ascending dose study (Study 1001). The interval between the IV loading dose and the SC maintenance doses was chosen such that the CSL312 plasma trough concentration after the IV loading dose would be within 20% of the trough concentration at steady-state after SC doses given every 4 weeks. The IV route of administration was selected for the loading dose as CSL312 plasma concentrations higher than the trough concentrations observed at steady state after SC doses given every 4 weeks are expected to be achieved instantaneously. The IV loading doses selected for this study are expected to result in exposures that are similar to the exposures after SC doses given the ~50% bioavailability of CSL312 when administered SC based on the results from phase 1 single ascending dose study (Study 1001).

A dose of CCI [REDACTED] mg q2wk for subjects with C1-INH HAE in the open-label arm of the study was selected to explore a dosing interval of 2 weeks. This dosing regimen was chosen to target a % inhibition of $\geq 90\%$ of the CCI [REDACTED].

A dose of [REDACTED] mg q4wk was selected for subjects with FXII/PLG HAE to provide the maximum potential benefit of treatment with a target of $\geq 90\%$ inhibition of their [REDACTED].

The maximum dose (IV or SC) and the predicted corresponding C_{max} in this study is lower than the highest administered dose (IV or SC) and its corresponding C_{max} observed in the phase 1 study, which were associated with acceptable safety findings.

